**Document Date: October 12, 2022**

## **Introduction**

Colorectal cancer (CRC) is the third most commonly diagnosed cancer in recent years, and the second leading cause of cancer death globally. In 2020, CRC accounts for 10% of global cancer incidence and 9.4% of cancer deaths, just lower than lung cancer. The global number of new CRC cases is predicted to reach 3.2 million in 2040 (1, 2).

Oxaliplatin is a third-generation platinum-based chemotherapy drug that is considered a key drug in treatment of colorectal cancer (3). The most reported adverse effect of oxaliplatin is neurotoxicity. Oxaliplatin induces two forms of peripheral sensory neuropathy. The first is transient, acute neuropathy usually resolves spontaneously within days. The second form is chronic cumulative poorly reversible peripheral neuropathy that worsens with the repetition of chemotherapy cycles (4).

Although a number of interventions have been implicated, none of them can be recommended for clinical use (5). This therapeutic failure reflects poor understanding of the real mechanism of oxaliplatin-induced neuropathy (6). However, oxidative stress is identified to be one of the main bio-molecular dysfunctions in this neuropathy (7).

This oxidative stress can trigger inflammatory reaction which in turn up-regulates the expression of pro-inflammatory cytokines like tumor necrosis factor- $\alpha$  (TNF- $\alpha$ ), interleukin-1 $\beta$  (IL-1 $\beta$ ), and interleukin-6 (IL-6), which has been well demonstrated to play an important role in the establishment and maintenance of the spinal cord sensitization, resulting in hyperalgesia, and finally inducing neuropathic pain (8). Neurotensin (NT) is an endogenous neuropeptide involved in modulation of pain signal transmission and perception (9, 10). There is a significant increase in NT level in rats treated with oxaliplatin (11).

Intestinal mucositis, or damage to the intestinal mucosa, is a major contributor to the reduced quality of life, decreased survival rates, and early onset of death observed in patients with certain chemotherapeutic agents (12). Citrulline is an amino acid mainly produced by enterocytes of the small bowel. Decreased levels of plasma citrulline are correlated with significant epithelial small bowel loss (13).

Pentoxifylline (PTX), a xanthine derivative, has been shown to have a marked effect on cellular mediators of inflammation and tissue injury. It has been shown to inhibit TNF- $\alpha$  production, possibly via inhibition of TNF $\alpha$  and IL-1 mRNA transcription with relative preservation or even an increase of IL-10, an anti-inflammatory cytokine (14, 15).

## **Aim of the work**

This study aims to:

- Evaluate the possible protective effect of pentoxifylline against oxaliplatin induced peripheral neuropathy and chemotherapy induced mucositis in patients with stage II and stage III colorectal cancer.

## Patients and Methods

### **- Study design and treatment protocol:**

This study will be a randomized placebo controlled parallel study. Forty-eight eligible patients with stage II and stage III colorectal cancer will be scheduled to receive 12 cycles of folinic acid, fluorouracil and oxaliplatin (FOLFOX6 regimen). Patients will be recruited from the Oncology Department, Tanta University Hospital, Tanta, Egypt. Staging will be done according to the American Joint Committee on Cancer 7th edition staging. The patients will be randomized using according to the days of hospital admission into two groups:

**Group I (control group; n=24)** which will receive 12 cycles of FOLFOX-6 regimen plus placebo tablets twice daily.

The chemotherapy cycles will be received every 2 weeks and will be as follows:

**Day 1:** Oxaliplatin 85 mg/m^2 intravenous infusion in 250-500 mL 5% dextrose solution and leucovorin 400 mg/m^2 intravenous infusion in 5% dextrose solution both were given over 120 minutes at the same time in separate bags using a Y-line access, followed by 5-fluorouracil 400 mg/m^2 intravenous bolus given over 2-4 minutes, followed by 5-fluorouracil 2400 mg/m^2 intravenous infusion in 1000 mL 0.9% Sodium Chloride solution as a 46-hour infusion.

Additionally, Intravenous 5-HT3 antagonist plus pantoprazole will be administered to all participants before each cycle as prophylactic therapy against chemotherapy induced nausea, vomiting and mucositis. Furthermore, all participants will be submitted to complete blood count analysis before each chemotherapy cycle.

**Group II (Pentoxifylline group; n=24)** which will receive FOLFOX-6 regimen in addition to pentoxifylline 400 mg twice daily.

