#### **- Ethical approval:**

The study will be performed in accordance with the ethical standards of Helsinki declaration in 1964 and its later amendments. The study will be approved by the Research Ethics Committee of Tanta University. The study will be registered as a clinical trial at ClinicalTrials.gov. All participants will be informed about the benefits and risks of the study. Any unexpected risks that will appear during the course of the research will be clarified to the participants and to the ethical committee on time. The data of the enrolled patients will be confidential. All enrolled patients will give their written informed consents. The study will be conducted between October 2022 and October 2024.

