## **D. Assessment of participants' adherence, side effects and tolerability**

Pentoxifylline will be provided on biweekly basis and the participants' adherence will be assessed through counting the returned tablets. Participants will be followed-up by weekly telephone calls and direct meetings during chemotherapy cycles to assess their adherence and to report any drug related adverse effects. The adverse effects will be collected and graded according to the National Cancer Institute Common Terminology Criteria for Adverse events "NCI-CTCAE; version 5, 2017" (17). Participants will be considered non-adherent and excluded from the study if not consumed the provided tablets or lost the follow-up meeting at any time of intervention or changed regimen.

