**- The primary and secondary endpoints:**

The primary endpoint is the percentage of patients with peripheral sensory neuropathy grade  $\geq 2$ , the variation of 12-item neurotoxicity questionnaire (Ntx-12) total score and the variation in grades of mucositis. The secondary endpoint is the change in the serum concentrations of the measured biological markers.

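### The trial is called randomized, but the only allocation rule is the day of hospital admission, with no random sequence, concealment or blinding roles described

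*Combined protocol and SAP*

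**What the plan says.** The study design section labels the trial: "This study will be a randomized placebo controlled parallel study". It then gives one allocation rule: "The patients will be randomized using according to the days of hospital admission into two groups". The sentence is garbled, and a method may have dropped out after the word using, but none is named there or elsewhere in the supplied text.

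On masking, the control arm receives chemotherapy "plus placebo tablets twice daily". Nothing says that the placebo matches, and no blinding or masking term appears. The adherence section mentions supply of the active drug only: "Pentoxifylline will be provided on biweekly basis".

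On consent, the ethics section says "All enrolled patients will give their written informed consents", without placing consent before or after allocation.

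The aim is causal: "Evaluate the possible protective effect of pentoxifylline against oxaliplatin induced peripheral neuropathy". The primary endpoint has three parts: the percentage with sensory neuropathy of grade 2 or worse, and "the variation of 12-item neurotoxicity questionnaire (Ntx-12) total score and the variation in grades of mucositis".

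**The concern.** Day of admission is a calendar fact that staff can see. If it fixes the arm, a recruiter who knows or infers the link between day and arm can tell which arm a patient would enter, and can enrol, defer or decline accordingly. The documents do not say whether recruiters would know the link. If days were drawn at random and kept hidden, the first patient on a given day could not be foreseen, but later patients on that day could.

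Two mechanisms are at stake, and they are separate.

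1. **Selection at entry** changes who is in each arm. It could distort all three primary outcomes, including the patient-reported Ntx-12, even if the tablets were perfectly masked. The placebo does not protect against it.
2. **Assessment.** Someone grading neuropathy or mucositis by CTCAE who knows the day rule could be influenced by it.

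The Statistical analysis section compares the arms by chi-square, unpaired t-test or Mann-Whitney, all without covariates. None of these would correct an imbalance created at entry.

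**Working it through.** **What the text contains.** Reading from the Introduction to the references for the elements of an allocation procedure:

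| Element | Found |
|---|---|
| Random sequence (list, blocks, strata) | No |
| Which days map to which arm | No |
| Concealment (central system, envelopes, coded packs) | No |
| Person responsible for assignment | No |
| Order of eligibility, consent and assignment | Not stated |
| Placebo | Named; matching not described |
| Who is blinded | No |

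**The plan's own figure.** The enrolled total of 48 follows from 41 evaluable patients and 15% attrition: 41/0.85 = 48.2, or 41 × 1.15 = 47.15. It is not in dispute here. The 24:24 split, however, does not follow from a day rule. If each patient's arm were an independent 50:50 outcome of the admission day, an exact 24:24 split would have probability C(48,24)/2^48 = 11.5%. A further rule is needed and is not stated.

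**Illustration of size (all inputs assumed).** No drug effect; 48 patients, split equally at random to begin with; half are high risk. Patients seen as high risk and due pentoxifylline move to control with probability f. Patients seen as low risk and due control move to pentoxifylline with probability f.

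With perfect recognition the expected high-risk share is (1 − f)/2 on pentoxifylline and (1 + f)/2 on control, a difference of f. The spurious differences are then:

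- Neuropathy of grade 2 or worse, risks 70% and 30%: f × (0.70 − 0.30) = 0.4f, which is 0.20 at f = 0.5 (simulated 0.202).
- Ntx-12, high-risk patients 0.8 SD worse: 0.8f, which is 0.16 SD at f = 0.2 and 0.40 SD at f = 0.5 (simulated 0.404).

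With 75% recognition the share differs by f × (0.75 − 0.25) = 0.5f. At f = 0.5 that is 0.25, so risks of 60% and 40% give 0.25 × 0.20 = 0.05, and a 0.4 SD gap gives 0.25 × 0.4 = 0.10 SD.

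Type I error (%) from 100,000 simulated null trials per setting, with rejection at p ≤ 0.05 and a Monte Carlo standard error of at most about 0.15 percentage points:

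| Test and setting | f = 0 | 0.1 | 0.2 | 0.3 | 0.5 |
|---|---|---|---|---|---|
| Chi-square, 70/30, perfect recognition | 6.1 | 6.9 | 9.8 | 14.6 | 30.5 |
| Chi-square, 70/30, 75% recognition | 6.0 | 6.2 | 6.8 | 7.9 | 11.5 |
| Chi-square, 60/40, perfect recognition | 6.1 | 6.1 | 6.7 | 7.8 | 11.8 |
| Chi-square, 60/40, 75% recognition | 5.9 | 5.9 | 6.0 | 6.2 | 7.1 |
| t-test, 0.8 SD, perfect recognition | 5.0 | 5.7 | 8.0 | 11.9 | 25.2 |
| t-test, 0.8 SD, 75% recognition | 5.0 | 5.3 | 5.8 | 6.7 | 9.8 |
| t-test, 0.4 SD, perfect recognition | 5.0 | 5.3 | 5.8 | 6.9 | 10.2 |
| t-test, 0.4 SD, 75% recognition | 5.0 | 5.0 | 5.3 | 5.5 | 6.3 |

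The chi-square test is uncorrected, which is why it starts near 6% with no steering. For its first row, using 41 patients instead gives 6.1, 6.9, 9.2, 13.6 and 27.3. Independent 50:50 initial assignment gives 5.7, 6.5, 9.6, 14.5 and 30.7.

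**Check by formula.** For a shift of b SD with n per arm, the rejection rate is Φ(b/s − 1.96) + Φ(−b/s − 1.96), with s = √(2/n). At n = 20.5, s = 0.312, and b = 0.1, 0.2, 0.3 and 0.5 give 6.2%, 9.8%, 16.1% and 36.0%. The simulated figures are of the same order.

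**The case against.** The best case for the plan has five parts.

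- **The sentence is damaged, and a proper method may be missing from it.** That is possible, and it is why the sponsor should be asked first. But the surviving words tie allocation to admission day, and no sequence or concealment appears elsewhere to override them.
- **The placebo arm implies an intention to mask.** It does, and the grader who knows the day rule is hypothetical. The missing blinding roles are therefore secondary to the allocation rule. Masked tablets do not conceal allocation.
- **Eligibility may come first.** The design section speaks of eligible patients before it mentions randomization. This order is not excluded, so it is not established that the admission day is known before eligibility and consent are settled. The remaining point is that no order is stated, and a recruiter who knows the rule could still influence who consents.
- **The exclusion criteria remove much visible risk.** They exclude, among others, patients with diabetes, pre-existing neuropathy, recent neurotoxic chemotherapy, smoking or neuroprotective drugs. This stands against the severe scenarios and makes the weaker rows more relevant. It narrows visible risk but does not abolish it: age and stage still vary.
- **The simulation is stylised.** It moves patients between arms rather than modelling deferral, and realised arm sizes drift (at 20% steering only about 20% of trials end 24:24). The expected movement is equal in both directions (12f each way), so the average difference does not come from the drift. If Ntx-12 is analysed as change from baseline, stable baseline differences cancel, and the assumed gap must be read as a gap in worsening.

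These points limit the illustration and one remark on timing. They do not make a calendar rule unpredictable.

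**Conclusion.** The concern holds. Followed as written, the protocol gives day-based, quasi-random allocation that staff could foresee, under the label of a randomized trial. This is a fault in the stated rule and not only missing detail, and it underlies every comparison between the arms.

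Confidence is high that no adequate method is described. Whether the sponsor intended something better cannot be told from the text.

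Selection bias is a risk here, not a demonstrated effect. On the assumed inputs, slight steering does little, while moderate steering on a strong, visible risk factor multiplies the false-positive rate about fivefold (6.1% to 30.5%; 5.0% to 25.2%). The need for change rests on the design principle and not on the worst scenario, because later analysis cannot reliably repair a predictable allocation.

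**What to change.** First ask the sponsor which allocation method was intended. Then replace the sentence with wording such as:

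> Patients will be randomized 1:1 by a computer-generated list in permuted blocks of varying size, prepared and held by someone not involved in recruitment or assessment (for example the pharmacy). The list will be concealed in sequentially numbered identical packs, assigned only after eligibility, consent and baseline assessment. Day of admission plays no part.

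Other concealed methods, such as a central system, would also serve. State who is blinded (patients, recruiters, those grading CTCAE) and that the placebo matches.

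The ethics section says "The study will be conducted between October 2022 and October 2024", so some or all patients may already have been allocated by day. If so, describe that part as quasi-randomized, report it separately from patients allocated by the new list, and limit the causal conclusion accordingly.

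**Cost.** A wording change, a list and pharmacy work. If one coded pack is issued per cycle in both arms (an assumption), that is 48 × 12 = 576 packs, and a matching placebo is needed. If the list is in place before enrolment, no extra patients, visits or procedures are required. If part of the sample was already allocated by day, the properly randomized part may fall below the 41 evaluable patients that the sample size section calls for, and that loss of precision should be stated.

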#### **- Ethical approval:**

The study will be performed in accordance with the ethical standards of Helsinki declaration in 1964 and its later amendments. The study will be approved by the Research Ethics Committee of Tanta University. The study will be registered as a clinical trial at ClinicalTrials.gov. All participants will be informed about the benefits and risks of the study. Any unexpected risks that will appear during the course of the research will be clarified to the participants and to the ethical committee on time. The data of the enrolled patients will be confidential. All enrolled patients will give their written informed consents. The study will be conducted between October 2022 and October 2024.

#### **- Inclusion criteria:**

- Patients with histologically confirmed diagnosis of stage II and stage III colorectal cancer.
- Patients who will be scheduled to receive FOLFOX-6 regimen.
- Patients with no contraindication to chemotherapy.
- Males and females aged  $\geq 18$  years old.
- Adequate baseline hematologic values (absolute neutrophilic count  $\geq 1.5 \times 10^9/L$ , platelet count  $\geq 100 \times 10^9/L$  and hemoglobin level  $\geq 10$  g/dl).
- Patients with adequate renal function (serum creatinine  $< 1.5$  mg/dL and Creatinine clearance (ClCr)  $> 45$  mL/min).
- Patients with adequate liver function (serum bilirubin  $< 1.5$  mg/dl).
- Patients with performance status  $< 2$  according to Eastern Cooperative Oncology Group (ECOG) score.

#### **- Exclusion Criteria:**

- Children  $< 18$  years old.
- Prior exposure to neurotoxic chemotherapy (oxaliplatin, cisplatin, vincristine, paclitaxel, docetaxel or Isoniazid) for at least 6 months prior the study treatment.
- Evidence of pre-existing peripheral neuropathy resulting from another reason (diabetes, brain tumor or brain trauma).
- Patients with diabetes and other conditions that predispose to neuropathy as hypothyroidism, autoimmune diseases or hepatitis C.
- History of known allergy to oxaliplatin or other platinum agents.

- Patients with other inflammatory diseases (rheumatoid arthritis and ulcerative colitis) or stressful conditions (obesity class 2 and 3, smoking).
- Concomitant use of multivitamins (vitamins E, C and A), tricyclic antidepressants or other neuro-protective medications (gabapentin, lamotrigine, carbamazepine and phenytoin, etc...).
- Concurrent active cancer originating from a primary site other than colon or rectum.
- Patients on blood thinning agents
- Pregnant and breastfeeding women

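### Blood-thinner use bars entry, but the plan does not say whether the bar holds during treatment, has no step to detect a new start, and could lose the outcome data of a participant whose tablets are stopped for it

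*Combined protocol and SAP*

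**What the plan says.** All references are to the combined protocol and SAP.

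- **Exclusion Criteria.** One item reads "Patients on blood thinning agents". No reason is attached. Another item in the same list is worded as ongoing use: "Concomitant use of multivitamins (vitamins E, C and A), tricyclic antidepressants or other neuro-protective medications". Blood thinners are not in that item.
- **Study design and treatment protocol.** The control group is one "which will receive 12 cycles of FOLFOX-6 regimen plus placebo tablets twice daily"; the other group receives "FOLFOX-6 regimen in addition to pentoxifylline 400 mg twice daily". On timing: "The chemotherapy cycles will be received every 2 weeks". A full blood count precedes each cycle; no coagulation test is listed.
- **Measurements, part A.** A medication history is taken with the demographic data and physical examination. No repeat is scheduled.
- **Measurements, part D (adherence, side effects and tolerability).** Participants have "weekly telephone calls and direct meetings during chemotherapy cycles to assess their adherence and to report any drug related adverse effects". Those judged non-adherent are "excluded from the study if not consumed the provided tablets or lost the follow-up meeting at any time of intervention or changed regimen".
- **Statistical analysis.** Reported adverse effects are compared with Fisher's exact test. No analysis population is defined.

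No section lists medication prohibited during the study or says what happens if a blood-thinning agent is started after enrolment.

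**The concern.** A drug-related entry bar usually reflects something the authors want to avoid while the study treatment is being taken. Here it is written only as a condition of entry, and treatment then runs for months. Three things are at stake.

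1. **Detection.** A new blood thinner could go unrecorded, so nobody could say afterwards who took the combination that the plan refuses at entry, or for how long.
2. **Safety comparison.** The contacts are set up to capture effects attributed to the drug. A bleed that the site attributes to the blood thinner or to chemotherapy may not be recorded, and so may not reach the comparison between arms.
3. **Outcome data.** If a clinician stops the tablets because a blood thinner is needed, the adherence rule on its literal wording removes the participant. The neuropathy and mucositis data would then be lost for a reason linked to safety. If such stops are more common in one arm, the comparison of the primary endpoints is biased.

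**Working it through.** **Side-by-side reading**

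| Question | What the plan provides |
|---|---|
| Is a patient on a blood thinner admitted? | No (Exclusion Criteria) |
| Does the bar apply after enrolment? | Not stated |
| Would a new start be detected? | No scheduled step: medication history has no stated repeat; contacts cover adherence and adverse effects |
| Are tablets continued or stopped after a new start? | Not stated |
| What happens to the participant if they are stopped? | Literal reading of part D: tablets not consumed, so excluded |
| Is bleeding counted whatever its cause? | Not stated; contacts refer to drug-related effects |

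**Length of exposure.** 12 cycles × 2 weeks = 24 weeks. Cycle 12 starts 11 × 2 = 22 weeks after cycle 1. This is derived; the plan gives no tablet duration in weeks.

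**Arm size.** The plan states 48 patients, 24 per arm, from 41 with 15% attrition. Check: 41 / (1 − 0.15) = 48.2, and 41 × 1.15 = 47.15. Both are close to 48, so 24 per arm is used below. The attrition allowance is 48 − 41 = 7 patients.

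**Possible co-exposure.** The documents give no rate of starting a blood thinner. Let *r* be the proportion who start one during the 24 weeks. The values below are assumptions.

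- Expected number in the pentoxifylline arm: 24*r*
- Chance of at least one in that arm: 1 − (1 − *r*)^24
- Expected number in both arms: 48*r*

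| Assumed *r* | 24*r* | 1 − (1 − *r*)^24 | 48*r* |
|---|---|---|---|
| 2% | 0.48 | 0.384 | 0.96 |
| 5% | 1.2 | 0.708 | 2.4 |
| 10% | 2.4 | 0.920 | 4.8 |

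Only the pentoxifylline arm can have true co-exposure. The last column matters for data loss, because placebo patients also take study tablets and fall under the same adherence rule. If every new starter had tablets stopped and was then excluded, about 1 to 4.8 of the 7 patients allowed for attrition would be used up in this way. That is an upper bound at each assumed rate, since the plan does not say that tablets would be stopped.

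**The case against.** The case against has several parts, and much of it stands.

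- **A reader might infer that the two sections contradict each other.** They do not. Part D says nothing about blood thinners, and its removal rule defines non-adherence. It is not presented as a complete list of reasons for withdrawal. The plan is silent rather than inconsistent.
- **A reader might infer that a patient who starts a blood thinner stays on tablets to the end.** The plan does not instruct continuation, and a treating clinician's judgement is not ruled out. A broad reading of a changed regimen might even reach a new drug, although the chemotherapy or study regimen is the more natural meaning.
- **A reader might infer that the exclusion is there because of bleeding risk.** The criterion gives no reason. The Introduction describes pentoxifylline's effect on inflammatory mediators, not on coagulation, and other exclusions look like control of confounding.
- **Other routes exist.** Weekly contacts, graded adverse effects, blood counts before each cycle and the commitment under Ethical approval to report unexpected risks could all bring a bleed to light. The Fisher's test item does not itself restrict effects to drug-related ones. This is fair, but none of these is a medication check, and the test can use only what the contacts collect.
- **The gap is not unique to blood thinners.** Pregnancy, tricyclics and neuroprotective drugs can also arise after entry. This is true, and one general rule on concomitant medication could cover them all. It does not remove the need to answer the question here.

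What the objections leave untouched is the missing detection step, the filter on adverse effects and the literal effect of the non-adherence rule.

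**Conclusion.** The point holds as an omission with practical consequences. The plan does not say whether its bar on blood-thinning agents continues during about 24 weeks of study tablets, and it provides no means of finding a new start. The adherence section adds two problems: adverse effects are sought according to presumed cause, and a participant whose tablets are stopped would be excluded on the literal wording.

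The size is uncertain. At assumed rates of 2% to 10%, about 0.5 to 2.4 of 24 pentoxifylline patients would be co-exposed. The probabilities of 38% to 92% for at least one case might be read as a risk of harm. They are not: they follow wholly from the assumed rates and describe exposure, and the documents contain no bleeding rate from which harm could be estimated.

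The conclusion rests on the absence of any rule in the text available and on reading the non-adherence sentence as it is written. It does not depend on the reason for the exclusion. The matter merits a short amendment; it does not undermine the design.

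**What to change.** 1. **Reconcile the Exclusion Criteria with part D of Measurements.** State whether the bar on blood-thinning agents applies while study tablets are taken, and refer to the procedure for a participant who comes to need one. The clinical rule is for the investigators.
2. **Detect.** Add one question to the existing weekly contacts, in both arms: has any blood-thinning agent been started, and if so its name and dates.
3. **Count.** Ask about bleeding by name, record every event with its grade, and tabulate by arm whatever the presumed cause.
4. **Retain.** State that a participant who starts a blood thinner, or whose tablets are stopped for that reason, remains in the scheduled neuropathy and mucositis assessments and in the analysis in the assigned group, and is not removed as non-adherent.

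**Cost.** A short protocol amendment and slightly more data collection at contacts that already take place. If the investigators choose to interrupt tablets, keeping those participants in the analysis will dilute the treatment contrast a little. At the assumed rates this concerns about 0.5 to 2.4 patients in the pentoxifylline arm.
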